4.2. Secondary Efficacy Endpoints

- The time to conversion from AF from start of infusion.
- The proportion of patients with relapse of AF within 5 min (IRAF) following pharmacological or direct-current (DC) cardioversion.
- The proportion of patients in SR at $3\text{ h} \pm 1\text{ h}$ after start of infusion.
- The proportion of patients in SR at $24\text{ h} \pm 2\text{ h}$ after start of infusion.
- The proportion of patients in SR at $30\text{ days} \pm 5\text{ days}$ after start of infusion.

4.3. Exploratory Endpoints

- Correlation of drug exposure (plasma Cmax and area under the concentration time curve [AUC]) and the time of conversion.
- Correlation of atrial size and conversion rate.
- Correlation of atrial size to relapse or failure.
- Correlation of gender and age and conversion rate.
- Correlation of duration of current AF, conversion rate and - sinus rhythm at some timepoint .

4.4. Pharmacokinetic Endpoints

The PK endpoints are as follows:

- Systemic exposure derived from the population PK model.
- Population PK model parameter estimates derived from plasma concentrations of AP30663.

Concentration-derived PK parameters of plasma AP30663 will be determined using 2 approaches:

- A static analysis based on plasma concentration will be performed using a non-compartmental analysis (NCA);
- PK parameters will also be derived using a non-linear mixed-effect modeling approach.

4.5. Safety Endpoints

- Adverse events (AEs), electrocardiogram (ECG) variables including significant arrhythmia, physical examination, vital signs, and laboratory evaluations.
- Changes in QTcF interval data over time.

This document is confidential.

5. Analysis Sets

For purposes of analysis, the following populations are defined for both Parts 1 and 2.

5.1. Enrolled Set

The Enrolled Set will include all patients who sign the ICF. Unless specified otherwise, this set will be used for patient listings and for summaries of patient disposition. This set will include screen failures.

5.2. Randomised Set

The Randomised Set will include all patients who signed the ICF and were subsequently randomised into the study (Screen failure are excluded), regardless of study treatment administration.

5.3. Full Analysis Set

The Full Analysis Set will serve as the primary population for the analysis of efficacy and will consist of all randomised participants who were administered double-blind study treatment and have an evaluable AF conversion status within 90 min from the start of infusion.

Patients will be analysed according to the randomised treatment.

5.4. Per Protocol Set

The Per-Protocol Set includes all patients from the Full Analysis Set who have been treated according to the protocol and fulfil the following criteria:

1. All inclusion/exclusion criteria satisfied according to the latest AP30663-2001 Protocol Version 4.0
2. Absence of relevant protocol violations with respect to factors likely to affect the efficacy of treatment where the nature of protocol violation will be defined before breaking the blind
3. Adequate study drug compliance, which will be determined before breaking the blind

Patients will be analysed according to the randomised treatment.

5.5. Safety Set

All randomised patients who were administered double-blind study treatment. Patients will be analysed according to the treatment received. The Safety Set will be used for all analyses of safety endpoints.

5.6. Pharmacokinetic (PK) Set

The PK Set will include all patients in the Safety Set who have at least one evaluable post-infusion drug concentration value.

5.7. Protocol Deviations

Important protocol deviations will be collected in the eCTMS. Each instance of a protocol deviation will be reviewed by the Sponsor and determined to be either major or minor before DBL.

The major protocol deviations include, but are not limited to the following (to be finalized before DBL):

This document is confidential.

- Eligibility deviations (Inclusion/Exclusion criteria)
- Improper reconstitution and administration of study medication
- Noncompliance with study medication (stop of drug infusion prior to 30 min)
- Noncompliance with study procedures if the consequence of noncompliance would compromise either the patient's safety and/or the study integrity, primary endpoint, and/or is not in line with GCP/ICH guidelines
- Use of prohibited concomitant therapies

Patients with any major protocol deviations that likely affect the efficacy of treatment will not be included in the PP population.

Number (%) of patients with at least one major protocol deviation will be included in a summary table, using the Randomised Set.

All protocol deviations will be listed for all patients in the Randomised Set, including their assignment of minor, major or critical, and the date the deviation occurred.

This document is confidential.

6. General Aspects for Statistical Analysis

6.2. Key Definitions

6.2.1. Baseline Value

Unless otherwise specified, the baseline value for any variable will be the last value taken prior to the infusion of the double-blind study treatment on Day 1. This includes pre-dose Day 1 assessments.

6.2.2. Last assessment

Unless otherwise specified, last assessment is defined as Day 30 visit or early discontinuation visit.

This document is confidential.

6.3. Missing Data

Unless otherwise specified, no imputation will be performed for missing data.

6.3.1. Missing Dates for prior or concomitant medications

For prior and concomitant medications with incomplete dates, the following rules will be used to impute start and/or stop dates for the purposes of determining whether a medication is prior or concomitant only.

- For start dates:
 - if day is missing the first day of the month will be used.
 - If day and month is missing, 1st of January will be used.
 - If the start date is missing completely, the date of infusion will be used.
 - If the stop date is complete and the imputed start date is after the actual stop date, then the start date will be imputed as the stop date.
- For stop dates:
 - if the day is missing then the last day of the month will be used.
 - If the day and month is missing, then 31st December will be used.
 - If the stop date is completely missing, then the date of infusion will be used. If the start date is complete and the imputed stop date is earlier than the actual start date, the stop date will be imputed as the start date.

6.3.2. Missing Dates for adverse event

If the adverse event start date is partially or completely missing, then the following rules will be used to impute the start date for the purposes of determining treatment emergence status only :

- If the whole start date is missing then the date of infusion will be used.
- missing month : if the AE has occurred the same year as the date of infusion, replace the missing month of onset by the month of date of infusion.
 - If the AE has occurred the subsequent year after the year of date of infusion, replace the missing month of onset by January.
 - If the AE has occurred the previous year of the year of date of infusion, replace the missing month of onset by December.
- missing day : replace it by '01', and verify that the completed date is greater or equal to the date of infusion. If not, replace the incomplete date of onset by the date of infusion.

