- n ECG print-outs: within 15 min before infusion start, at 10 min after infusion start, and, in case of conversion from AF, within 1 min after conversion BUT before infusion stop. Diagnosis of AF (defined as absence of discrete P waves and an irregular ventricular rate) to be confirmed based on a 12-lead ECG. On Day 2 the ECG should be completed 24 h +/- 2 hours after infusion start.
- o Continued assessment to start 30 min before infusion. Holter to stop after the PK sampling at 8 h. Telemetry to continue for minimum 8 h after infusion start.
- p Should be done in all patients; mandatory if not done within 6 months (inclusive) before randomisation.
- q Heart rhythm, LV size, LV area, LVEF, atrial area and size as well as other clinically significant finding results to be provided or requested if available.
- r In case of AF persistence at 90 min after start of infusion, a direct-current electrical cardioversion is to be done within 180 min post-infusion start (200 J biphasic synchronised).
- s Recording of any AEs/SAEs will start after the ICF has been signed. From infusion start, special attention should be paid to AEs related to the central nervous system including tremors.

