9.7 Duration of Treatment

Study drug infusion is planned for 30 min for each patient.

Regardless of which study part (Part 1 or 2) the patient participates in, the overall study duration for each patient is up to a maximum of 42 days. The screening and randomisation will occur within 7 days (inclusive) from onset of AF. The duration of treatment and post-treatment follow-up will be 30 days ± 5 days from start of infusion to the follow-up visit.

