10.3. Adverse Events / Adverse Drug Reactions

AEs will be coded using the Medical Dictionary for Regulatory Activities (MedDRA) version 21.1 or an updated version. Summaries will be presented by system organ class (SOC) and preferred term. Treatment-emergent AEs (TEAEs) are defined as any AE occurring or worsening on or after the first dose of study medication. Partial AE dates will be imputed.

The frequency and incidence of TEAEs will be presented by SOC and preferred term for each treatment group (number and percentage of patients experiencing at least one TEAE per preferred term as well as the number of observed events per preferred term; percentages will be based on the number of patients in the safety set).

The summaries presenting frequency of AEs by SOC and PT will be ordered by overall descending frequency of SOC and then, within a SOC, by overall descending frequency of PT.

Separate tables will be presented by severity and by relationship, and for SAEs, related TEAEs, and TEAEs leading to study discontinuation.

Relationships of 'very likely', 'probable' and 'possible' are to be considered as related to study drug for the summary tables. Relationships of 'unlikely' and 'unrelated' are to be considered not related to study drug.

In case of missing relationships, AEs will be considered as related.

All AEs will be presented in full in a comprehensive listing including patient number, treatment group, severity, seriousness, action taken, outcome, relationship to treatment, onset/stop, and duration. TEAEs will be flagged in the listings.

This document is confidential.

Details of SAEs and AEs leading to withdrawal will be listed separately.

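### The SAP's missing-day rule flags adverse events as treatment-emergent even when the recorded month, year or stop date places them before infusion

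*SAP*

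**What the plan says.** SAP 6.3.2 gives rules for partial or missing onset dates, to "impute the start date for the purposes of determining treatment emergence status only". Three of them matter here.

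- Missing day: "missing day : replace it by '01', and verify that the completed date is greater or equal to the date of infusion". The next sentence reads "If not, replace the incomplete date of onset by the date of infusion".
- Missing month, with a recorded year before the infusion year: "If the AE has occurred the previous year of the year of date of infusion, replace the missing month of onset by December".
- Wholly missing date: the infusion date is used.

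SAP 10.3 supplies the definition that the imputed date feeds: "Treatment-emergent AEs (TEAEs) are defined as any AE occurring or worsening on or after the first dose of study medication". It also confirms that "Partial AE dates will be imputed".

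Pre-infusion events do reach the database. A footnote to the schedule in Protocol 8.1.2 says "Recording of any AEs/SAEs will start after the ICF has been signed". The period in which they can arise is short, because under Protocol 9.7 "The screening and randomisation will occur within 7 days (inclusive) from onset of AF".

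The neighbouring rule for medications (SAP 6.3.1) moves an imputed start back to the stop date if it would otherwise fall after a complete stop date. Section 6.3.2 has no such check for adverse events.

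**The concern.** When an onset date is truly ambiguous, counting the event as treatment-emergent is ordinary caution. That covers an onset in the infusion month with the day unknown, or one with no date at all. The difficulty is that the missing-day step treats unambiguous dates in the same way. An onset recorded as the month before infusion, or the year before, is known to precede treatment whatever the day was, yet the rule moves it to infusion day. The December line suggests that the authors meant previous-year onsets to stay before infusion, and the missing-day step undoes this whenever the day is also absent.

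What is at stake is the content of the treatment-emergent tables. SAP section 16 marks three of them (14.3.1.1 overall, 14.3.1.3 related and 14.3.1.4 serious) for delivery at the interim analyses, and SAP 2.2 allows the DMC to stop a dose arm for unacceptable safety or tolerability. Arms are small at that stage. The examples in Protocol 17.3 show 6, 12 or 18 patients on a dose at an interim.

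**Working it through.** The plan gives no figure on this point, so there is none to reproduce. The check applies the rule as written and then bounds how often it can matter.

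**1. What the rule does to a missing day.** Let I be the infusion date and F the first day of the onset month, as recorded or as filled by the missing-month rule. The rule returns F if F ≥ I and I otherwise, so

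imputed onset = max(F, I) ≥ I.

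Under the definition in SAP 10.3 an onset on or after I is treatment-emergent. No event with a missing onset day can therefore be classed as pre-treatment. Running the rule over 730 infusion dates × 3 onset years (previous, same, next) × 13 month entries (1 to 12, or missing) = 28,470 combinations gave 0 classed as not treatment-emergent.

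**2. Worked dates.**

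| Recorded onset | Infusion | Imputed onset | Flag under the SAP | Flag under the fix |
|---|---|---|---|---|
| Feb 2022, day missing | 3 Mar 2022 | 3 Mar 2022 | TEAE | not TEAE |
| Dec 2021, day missing | 4 Jan 2022 | 4 Jan 2022 | TEAE | not TEAE |
| 2021, month and day missing | 4 Jan 2022 | 4 Jan 2022 | TEAE | not TEAE |
| 30th, 2021, month missing | 4 Jan 2022 | 30 Dec 2021 | not TEAE | not TEAE |
| 27 Feb 2022, complete | 3 Mar 2022 | none needed | not TEAE | not TEAE |
| Mar 2022, day missing | 20 Mar 2022 | 20 Mar 2022 | TEAE | TEAE |
| wholly missing | 3 Mar 2022 | 3 Mar 2022 | TEAE | TEAE |

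The first three rows are the error. The next two show its limits. The last two are ambiguous dates, which the fix leaves as they are (with no stop date before infusion).

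**3. Stop date.** Suppose onset is March 2022 with the day missing, the recorded stop is 18 March, and infusion is 20 March. The rule gives an onset of 20 March, two days after the event ended, and flags it. This route needs no month end.

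**4. How often an earlier month can arise.** If onset is L days before infusion and infusion dates are spread evenly over the year, onset falls in an earlier calendar month for the first L days of each of 12 months:

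share = 12 × L / 365.

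- L = 1: 12/365 = 3.3%
- L = 3: 36/365 = 9.9%
- L = 7: 84/365 = 23.0%

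Averaged evenly over L = 1 to 7 (mean 4, my assumption), the share is 48/365 = 13.2%. The 7 days run from AF onset to randomisation. Protocol 8.4.1 asks for infusion preferably within 12 h after that, and one extra calendar day (L = 8) would give 96/365 = 26.3%.

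These are shares of infusion dates. To reach a number of affected events they must be multiplied by the chance of an event between consent and infusion and the chance that its onset day is unknown. The documents give neither.

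**5. Effect of one misclassified event.** If the patient has no other event in the same table row, incidence moves by 1/6 = 16.7, 1/12 = 8.3 or 1/18 = 5.6 percentage points for arms of 6, 12 or 18.

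**The case against.** The strongest reply is that the rule will rarely, if ever, be triggered. Date of first occurrence is a required item for each event (Protocol 10.1.3.1), missing data are queried (Protocol 12.3), and events are recorded at screening and again at baseline, so recall covers only days. Randomisation is to follow consent and screening as soon as practicable, which makes a full 7-day gap unlikely. In at most 108 patients the number of affected events may be zero. All of this stands, and it sets the size of the point.

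A second reply is that the consequence is mild. The imputed date sets the flag only. Listings keep partial dates with dashes and show the treatment-emergent flag (SAP 14.2.5.3 and 10.3), so a reclassified event can be spotted. An event that began before dosing fits the protocol's description of an unrelated event, so it should stay out of the related table unless causality is missing, in which case SAP 10.3 counts it as related. The same rule applies in every arm, it errs towards over-counting, and the dose algorithm uses conversion rate only. This stands too. It does not justify a rule that overrides a recorded month, year or stop date.

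Two stronger readings should be resisted. A reader might infer that the December line has no effect at all. The reset sits only in the missing-day bullet, so the line still works when the day is known and only the month is missing. A reader might also take 23% as the share of patients affected. It is the share of infusion dates at which an onset a full 7 days earlier falls in the previous month, before the two unknown probabilities are applied.

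**Conclusion.** The rule is wrong as written, with very small expected impact. Taken literally, SAP 6.3.2 flags every adverse event with a missing onset day as treatment-emergent, including events whose recorded month, year or stop date places them before infusion. The December provision is defeated whenever the day is also missing.

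The earlier-month route is open for 3.3% to 23.0% of infusion dates for onsets 1 to 7 days before infusion. The upper figure is a ceiling that assumes a full 7-day gap, infusion dates spread evenly over the year, and no extra calendar day between randomisation and infusion. The stop-date route does not depend on a month end, and its frequency cannot be derived from the documents. Complete onset dates are unaffected, and so is efficacy. Nothing in the documents supports inferring bias between arms or a changed DMC decision.

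**What to change.** Amend the missing-day bullet in SAP 6.3.2 along these lines: substitute the infusion date only when the known month and/or year of onset match those of infusion, or are unknown, and the event did not end before infusion. If the known month or year is earlier than infusion, or the stop date is before infusion, classify the event as not treatment-emergent unless it worsened on or after infusion. Apply the stop-date condition to wholly missing onset dates as well.

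This keeps the cautious handling of ambiguous dates. It should not lose worsening events, since Protocol 10.1.3.1 requires a change in severity to be recorded as a separate event.

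The cost is a sentence or two in the SAP and a condition in the derivation program, with no change to data collection. If treatment-emergent tables have already been produced under the present rule, listing the adverse events with a missing onset day would show whether any were affected.

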6.4. Visit Windows

Not applicable

This document is confidential.

6.5. Pooling of Centres

Not applicable

6.6. Subgroups

No subgroup for this study.

This document is confidential.

7. Demographic, Other Baseline Characteristics and Medication

7.1. Patient Disposition and Withdrawals

The following frequencies (number and percent) will be displayed in the patient disposition table, by treatment group and overall:

Number of patients enrolled;

Number of patients screen failure;

Number of patients randomised;

Number (%) of patients in the FAS set (Full Analysis Set see definition in section 5);

Number (%) of patients in the PP set (Per-Protocol Set, see definition in section 5);

Number (%) of patients in the PK set (Pharmacokinetic Set, see definition in section 5);

Number (%) of patients in the Safety set (see definition in section 5);

Number (%) of patients who completed the study;

Number (%) of patients who discontinued the study early, and reasons for discontinuation.

The analyses of disposition will be based on the Enrolled Set. The denominators for the percent calculations will be the number of patients in the Randomised Set.

Table for Patient Disposition will be presented by cohort at each Interim analysis.

Patient completion status, date of completion/discontinuation and reason for discontinuation will be listed.

7.2. Demographic and Other Baseline Characteristics

Gender and child-bearing potential (female patients only), ethnicity will be summarized by the number and percentage of patients in each treatment group. Age (years) will be summarized using descriptive summary statistics.

Demographics parameters will be also presented by cohort at each Interim Analysis.

Data from transthoracic echo (TTE) will be presented using summary statistics. Height and baseline weight will be also summarized.

Duration of current AF episode (in hours) (derivation see section 8.1) and time since initial AF diagnosis (in years) will be summarized in addition.

Time since initial AF diagnosis (in years) = date of randomization – date of initial AF diagnosis (based on MHDECOD = 'Atrial Fibrillation')

In case of an incomplete date of initial AF diagnosis, the first day of the month will be used for a missing day, 1st January will be used for a missing day and month.

All demographic data will be presented in a data listing.

This document is confidential.

7.3. Medical History and Concomitant Diseases

Medical history will be coded to system organ class (SOC) and preferred term (PT) using Medical Dictionary for Regulatory Activities (MedDRA) version 21.1 or an updated version.

Data will be summarized by SOC and PT and sorted alphabetically. Conditions that are reported more than once for a given SOC and PT will be counted only once per patient on the PT level for each SOC

A corresponding data listing will be presented.

7.4. Medication

Section 6.3.1 describes how missing dates will be imputed for the purpose of determining prior/concomitant medication status.

7.4.1. Prior Medication

Prior and concomitant medications will be coded by the Anatomical Therapeutic Chemical (ATC) classification system according to the World Health Organization Drug Dictionary (WHODRUG), WHODrug Global B3 Sep 2018.

Prior medications will include medications started and stopped prior to the infusion date of the study drug.

For the summary tables, the count and percentage of patients under each anatomical therapeutic chemical (ATC) class level 2 and PT will be summarized by treatment group.
If a patient has taken prior medications more than once, the patient will be counted only once under any given drug class.

7.4.2. Concomitant Medication

Concomitant medications will include medication started on or after the infusion date of study drug.
Medication that started before the infusion of study drug and continued on or after the infusion date will be considered as concomitant medication.

For the summary tables, the count and percentage of patients under each anatomical therapeutic chemical (ATC) class level 2 and PT will be summarized by treatment group.
If a patient has taken concomitant medications more than once, the patient will be counted only once under any given drug class.

A listing of prior and concomitant medications will be provided for all patients in the safety set. A flag will be included in the listing to distinguish prior and concomitant medications.

This document is confidential.

8. Efficacy

